1.0 INTRODUCTION

This document is a clinical investigational plan (CIP) for a prospective, multi-center, single-arm, post-market study intended to support clinical follow-up of the CE-Marked Amplatzer Trevisio™ Intravascular Delivery System (Amplatzer Trevisio Delivery System). The device is intended for use with CE-Marked Amplatzer™ Occluder devices. This clinical study is sponsored by Abbott.

This clinical study will be conducted in accordance with this CIP. All investigators involved in the conduct of the clinical study will be qualified by education, training, or experience to perform their tasks and this training will be documented appropriately.

1.1 Background

The Amplatzer™ TorqVue™ Delivery System (ITV) has historically been used to facilitate the attachment, loading, delivery, and deployment of the Amplatzer Occluder devices. The Amplatzer Trevisio Delivery System is a new design iteration of the Amplatzer TorqVue delivery system with a redesigned delivery cable and a more flexible distal end, which is intended to impart less bias (i.e., tilt) on the occluder during the placement evaluation period before releasing the occluder from the delivery system. The delivery cable also has a proximal indicator to alert physicians when the occluder is approaching the end of the delivery sheath, which may reduce the use of fluoroscopy and patient exposure to radiation. All other components of the delivery system are identical to the currently marketed Amplatzer TorqVue Delivery System.

1.2 Rationale for Conducting this Clinical Study

The purpose of this study is to evaluate the safety and effectiveness of the design iteration of the Amplatzer™ TorqVue™ Delivery System—the Amplatzer Trevisio Delivery System—in a post-approval clinical setting. Data on the safety and effectiveness of the Amplatzer™ Trevisio Delivery System in patients undergoing closure of a patent foramen ovale (PFO), atrial septal defect (ASD), muscular ventricular septal defect (VSD), and post-infarct muscular VSD with Abbott's Amplatzer™ PFO Occluder, Amplatzer™ Septal Occluder (ASO), Amplatzer™ Multi-fenestrated Septal Occluder – “Cribiform” (ASD-MF), Amplatzer™ Muscular VSD Occluder, and Amplatzer™ Post-Infarct Muscular VSD Occluder will be collected. This study is intended to fulfill post-CE Mark requirements.

2.0 CLINICAL STUDY OVERVIEW

2.1 Clinical Study Objective

The primary objective of this clinical study is to characterize the safety and effectiveness of the Amplatzer Trevisio Delivery System for facilitating percutaneous, transcatheter implantation of the Amplatzer PFO Occluder, Amplatzer ASO, Amplatzer ASD-MF Occluder, Amplatzer Muscular VSD Occluder, and Amplatzer Post-Infarct Muscular VSD Occluder. The Amplatzer Trevisio Delivery System is CE-Marked and commercially available.

2.1.1 Name of the Device(s) Being Studied

The device being studied is the Amplatzer Trevisio Delivery System, which is used to facilitate implantation of Abbott's Amplatzer Occluder devices. Model numbers for the Amplatzer Trevisio Delivery System can be seen in Table 1. Refer to the Instructions for Use (IFU) for further detail about the delivery

[REDACTED]

[REDACTED]

Clinical Investigation Plan

system and occlusion devices (see Amplatzer Trevisio Intravascular Delivery System IFU; Amplatzer PFO Occluder IFU; Amplatzer Septal Occluder IFU; Amplatzer Multi-fenestrated Septal Occluder – “Cribiform” IFU; and the combined Amplatzer Muscular VSD Occluder and Post-Infarct Muscular VSD Occluder IFU).

Table 1. Device Name and Model Numbers

Device name (market-released)	Model/Type	Manufacturer
Amplatzer™ Trevisio™ Intravascular Delivery System	9-ATV06F45/60 9-ATV07F45/60 9-ATV07F45/80 9-ATV08F45/60 9-ATV08F45/80 9-ATV09F45/80 9-ATV10F45/80 9-ATV12F45/80 9-ATV13F45/80	Abbott Medical

2.1.2 Indication for Use

[figure not shown]
The Amplatzer Trevisio Intravascular Delivery System is intended to facilitate the attachment, loading, delivery and deployment of the Amplatzer Occluder devices.

2.1.3 Description of the Delivery System

The Amplatzer Trevisio Delivery System is designed to deliver Amplatzer Occluder devices. The delivery system is shipped separately from the occluders. The body of the delivery system sheath is radiopaque for visibility under fluoroscopy. The Amplatzer Trevisio Delivery System was sterilized with ethylene oxide and is for single use only. The more flexible delivery cable included in the Amplatzer Trevisio Delivery System will impart less bias (i.e., tilting) on the occluder during the placement evaluation period before releasing the occluder from the delivery system.

The components of the Amplatzer Trevisio Delivery System are shown in Figure 1. The Trevisio cable is offered in both 60 cm and 80 cm sheath lengths with a 45° curve and has the same French sizes as the Amplatzer TorqVue™ 45° Delivery System. Please refer to the IFU for additional information regarding the delivery system used in this clinical study.

Clinical Investigation Plan

- A. Loader – introduces the AMPLATZER™ Occluder into the sheath
- B. Hemostasis valve with extension tube and stopcock - Allows flushing of the delivery system and controls blood backflow.
- C. Sheath – Provides a pathway through which an AMPLATZER™ Occluder is delivered
- D. Dilator – Eases penetration of tissue and minimizes vessel trauma
- E. Delivery Cable – Attaches to the AMPLATZER™ Occluder to control its movement through the sheath, and releases the occluder upon deployment
- F. Cable Vise – Attaches to the delivery cable and serves as a handle for disconnecting (unscrewing) the delivery cable from an AMPLATZER™ Occluder.

Figure 1. Amplatzer Trevisio Intravascular Delivery System

2.1.4 Device Handling

Refer to the Amplatzer Trevisio Intravascular Delivery System IFU for more detail about proper handling, storage, and use requirements.

3.0 CLINICAL STUDY DESIGN

3.1 Purpose

The purpose of this prospective, multi-center, single-arm, post-approval study (PAS) is to characterize the safety and effectiveness of the Amplatzer Trevisio Delivery System.

3.2 Design overview

This PAS is a non-randomized, multi-center, single arm clinical study to evaluate the safety and effectiveness of the Amplatzer Trevisio Delivery System for facilitating percutaneous, transcatheter implantation of the Amplatzer PFO Occluder, Amplatzer ASO, Amplatzer ASD-MF Occluder, Amplatzer Muscular VSD Occluder, and Amplatzer Post-Infarct Muscular VSD Occluder.

A minimum of 215 subjects undergoing PFO or ASD closure will be enrolled from up to thirty (30) centers in Europe (at least 100 of these subjects must be undergoing PFO closure). In addition to the 215 subjects undergoing PFO or ASD closure, a minimum of

Clinical Investigation Plan

44 subjects undergoing muscular VSD or post-infarct muscular VSD closure will be enrolled. Subjects will be evaluated at baseline (pre-procedure), implant procedure, and prior to discharge or 7 days after the procedure, whichever occurs first. [REDACTED]

3.3 Clinical Study Procedures and Follow-up Schedule

Each subject will be assessed at baseline (pre-procedure), implant procedure, and prior to discharge or at 7 days, whichever occurs first. The study assessment flow chart is shown in Figure 2.

[figure not shown]

Figure 2. Clinical Study Flow Chart

3.4 Measures Taken to Avoid and Minimize Bias

This PAS is a non-randomized, multi-center, single arm clinical study. In order to minimize selection bias sites will make every effort to seek consent for participation from all eligible patients within their institution who are undergoing ASD, PFO, or VSD closure with the Amplatzer Trevisio Delivery System.

3.5 Suspension or Early Termination of the Clinical Study

No formal statistical rule for early termination of the clinical study for insufficient effectiveness of the device being studied is defined.

The Sponsor reserves the right to discontinue the clinical study at any stage with suitable written notice to the Principal Investigator. Possible reason(s) may include, but are not limited to:

- Sponsor oversight (e.g., Medical Director) decides to stop or terminate the clinical study due to a safety concern (such as higher frequency of anticipated adverse device effects)
- The study is no longer required by a regulatory authority, or the scope is reduced

Should the clinical study be discontinued by the Sponsor, subjects will be followed per routine hospital practice with device-related AEs reported to the Sponsor as per vigilance/commercial reporting requirements. Should this occur, the Principal Investigator shall return all clinical study materials to the Sponsor and provide a written statement to the EC (if applicable). All applicable clinical study documents shall be subject to the same retention policy as detailed in Section 10.5 of the CIP.

[REDACTED]

[REDACTED]

Clinical Investigation Plan

If the Sponsor suspends or prematurely terminates the clinical study at an individual site the Principal Investigator or authorized designee will promptly inform the enrolled subjects at his/her site, if appropriate.

A Principal Investigator, EC or regulatory authority may suspend or prematurely terminate participation in the clinical study at the study site(s) for which they are responsible. The investigators will follow the requirements specified in the Clinical Trial Agreement.

4.0 **ENDPOINTS**

The study has a primary effectiveness endpoint, a primary safety endpoint, and a number of descriptive endpoints.

4.1 **Primary Endpoints**

Primary Effectiveness Endpoint: Technical success – successful deployment and release of at least one device

Primary Safety Endpoint: Device- or procedure-related serious adverse events through discharge or 7 days, whichever occurs first, including:

- Cardiac perforation
- Sustained atrial fibrillation requiring intervention
- Device thrombus
- Device erosion
- Device embolization
- Vascular complication requiring surgical intervention
- Device- or procedure related serious adverse event leading to death

4.2 **Descriptive Endpoints**

- The number of times the device is recaptured
- The number of times the device is repositioned
- Total fluoroscopy time
- Ease of use – investigators will be asked survey questions about their first experience with the Amplatzer Trevisio Delivery System.

5.0 **SUBJECT SELECTION AND WITHDRAWAL**

5.1 **Subject Population**

This clinical study will enroll male and female adults and children with a PFO (adults only), ASD or VSD who are indicated for transcatheter closure. Patients must meet all general eligibility criteria and provide written informed consent prior to sites conducting any study-specific procedures not considered standard of care.

Clinical Investigation Plan

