5.4 Subject Enrollment

A subject is considered enrolled in the clinical study when the subject and the subject's legal representative (if applicable) provides written informed consent, has been confirmed to meet all inclusion criteria and none of the exclusion criteria, and implantation of an Amplatzer PFO Occluder, Amplatzer ASO, Amplatzer ASD-MF Occluder, Amplatzer Muscular VSD Occluder, or Amplatzer Post-Infarct Muscular VSD Occluder has been attempted with the Amplatzer Trevisio Delivery System, with implant attempt defined as the delivery system entering the subject's anatomy.

Clinical Investigation Plan

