8.2.1.1 PFO and ASD Closure Groups

The performance goal for the primary effectiveness endpoint for the PFO and ASD closure groups is set at 95% [REDACTED]

Let π_1 be the proportion of subjects who experience successful deployment and release of at least one device.

The following hypothesis will be tested:

$$H_0: \pi_1 \leq 95\%$$

$$H_a: \pi_1 > 95\%$$

[REDACTED]

The hypothesis will be tested at a one-sided significance level of 2.5% [REDACTED]

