This statistical analysis plan (SAP) is to provide a detailed and comprehensive description of the planned methodology and analysis to be used for ABT-CIP_10319, the Trevisio PAS clinical investigation. This plan is based on the Version A, 03 June 2020 Clinical Investigation Plan.

1.2 **Clinical Investigation Objectives**

The primary objective of this clinical study is to characterize the safety and effectiveness of the Amplatzer Trevisio Delivery System for facilitating percutaneous, transcatheter implantation of the Amplatzer PFO Occluder, Amplatzer ASO, Amplatzer ASD-MF Occluder, Amplatzer Muscular VSD Occluder, and Amplatzer Post-Infarct Muscular VSD Occluder. The Amplatzer Trevisio Delivery System is CE-Marked and commercially available.

1.3 **Clinical Investigation Design**

This post-approval study (PAS) is a non-randomized, multi-center, single arm clinical study to evaluate the safety and effectiveness of the Amplatzer Trevisio Delivery System for facilitating percutaneous, transcatheter implantation of the Amplatzer PFO Occluder, Amplatzer ASO, Amplatzer ASD-MF Occluder, Amplatzer Muscular VSD Occluder, and Amplatzer Post-Infarct Muscular VSD Occluder.

[REDACTED]

Subjects will be evaluated at baseline (pre-procedure), implant procedure, and prior to discharge or 7 days after the procedure, whichever occurs first. [REDACTED]

[REDACTED]

1.4 **Endpoints**

The study has a primary effectiveness endpoint, a primary safety endpoint, and a number of descriptive endpoints.

1.4.1 **Primary Effectiveness Endpoint**

The primary effectiveness endpoint is technical success, which is defined as successful deployment and release of at least one device.

Statistical Analysis Plan

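### The visible definition of technical success does not say that the occluder must be released with the Trevisio system, so read literally a Trevisio failure completed with another delivery system meets the endpoint

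*Protocol*

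**What the plan says.** Protocol 2.1.1 identifies the studied product: "The device being studied is the Amplatzer Trevisio Delivery System". The occluders are separate, already marketed products that it delivers.

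Protocol 4.1 gives the primary effectiveness endpoint as technical success, meaning "successful deployment and release of at least one device". Section 8.2.1 and Appendix IX repeat this. SAP 1.4.1 names technical success as the endpoint, "which is defined as successful deployment and release of at least one device". The tested parameter in the PFO/ASD cohort (Protocol 8.2.1.1, SAP 2.3.1.1) is "the proportion of subjects who experience successful deployment and release of at least one device". The VSD cohort uses the same words (Protocol 8.2.1.2, SAP 2.3.1.2).

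Trevisio comes in through enrolment. Under Protocol 5.4, a subject is enrolled when implantation "has been attempted with the Amplatzer Trevisio Delivery System, with implant attempt defined as the delivery system entering" the subject's anatomy. Release with Trevisio is not required.

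No visible text in either document says what happens to the endpoint if the operator changes to another delivery system.

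**The concern.** What is deployed and released is the occluder, and Protocol 6.2.1 also uses the word device for the occluder when it counts recaptures and repositionings. The endpoint therefore describes what happened to the occluder, while the study asks whether the delivery system works.

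Together with the attempt-based enrolment rule, this leaves a gap. A subject in whom Trevisio enters the body but cannot complete delivery is enrolled. If the operator then finishes with a different system (a conversion, below), an occluder has been released, and the literal definition is met. The alternative is a realistic one: Protocol 1.1 describes the earlier TorqVue system as still on the market and as differing only in the delivery cable.

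At stake is what the primary effectiveness test measures. Scored literally, it estimates the chance that a patient receives an occluder by some route after a Trevisio attempt. Scored as the objective implies, it estimates the chance that Trevisio delivers one. Sites or analysts could score the same case differently. The VSD cohort is the more exposed in design terms, since its sample size rests on this endpoint.

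**Working it through.** **Inputs from the documents**
- PFO/ASD: minimum N = 215 (Protocol 5.6.1), goal 95%, one-sided 2.5% (Protocol 8.2.1.1).
- VSD: minimum N = 44 (Protocol 5.6.2), goal 80%, one-sided 5% (Protocol 8.2.1.2).

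**Inputs that are assumptions**
- An exact one-sided binomial test, because the test method is not visible.
- The fraction f of Trevisio failures that are converted and scored as success. The documents give none, so a range is shown.

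**The plan's own figure.** N = 44 is sized on technical success (Protocol 8.3.2, SAP 2.4.2), but the assumed rate and power are redacted, so it cannot be reproduced. For context only, the test below has power 54.7%, 80.8% and 93.3% at true rates of 90%, 93% and 95%. N = 215 is sized on the safety endpoint.

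**Step 1: pass thresholds.** Find the smallest r with P(X ≥ r | N, goal) ≤ alpha.
- N = 215: P(X ≥ 211 | 0.95) = 0.0159, which is at most 0.025; P(X ≥ 210 | 0.95) = 0.0398, which is not. Passing needs 211 successes, so at most 215 − 211 = 4 failures.
- N = 44: P(X ≥ 40 | 0.80) = 0.0440, which is at most 0.05; P(X ≥ 39 | 0.80) = 0.1018, which is not. Passing needs 40 successes, so at most 44 − 40 = 4 failures.

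A score test gives the same cut-offs. For 211/215, z = (0.9814 − 0.95)/√(0.95 × 0.05/215) = 2.11, above 1.96; for 210/215, z = 1.80. For 40/44, z = (0.9091 − 0.80)/√(0.80 × 0.20/44) = 1.81, above 1.645; for 39/44, z = 1.43.

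**Step 2: effect of one subject.** Five Trevisio failures give 210/215 or 39/44, and both fail. If one of the five is converted and scored as success, the counts become 211/215 or 40/44, and both pass.

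**Step 3: pass probability with the Trevisio-only rate p exactly at the goal.** The scored success rate is s = p + (1 − p)f, and the pass probability is P(X ≥ r | N, s).

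| f | s, PFO/ASD | P(pass), PFO/ASD | s, VSD | P(pass), VSD |
|---|---|---|---|---|
| 0% | 0.9500 | 0.0159 | 0.80 | 0.0440 |
| 10% | 0.9550 | 0.0331 | 0.82 | 0.0825 |
| 25% | 0.9625 | 0.0919 | 0.85 | 0.1903 |
| 50% | 0.9750 | 0.3745 | 0.90 | 0.5472 |
| 75% | 0.9875 | 0.8660 | 0.95 | 0.9325 |

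The first row is the false-pass rate if every conversion is a failure. In both cohorts the nominal level (2.5% and 5%) is exceeded from f = 10% upwards.

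A rate below the goal can be masked too. With half of failures converted, a Trevisio-only rate of 93% passes with probability 0.1258 in PFO/ASD (s = 0.93 + 0.07 × 0.5 = 0.965), and a rate of 75% passes with probability 0.3418 in VSD (s = 0.75 + 0.25 × 0.5 = 0.875).

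**The case against.** The strongest reply is that the phrase should be read in context. The objective is the effectiveness of Trevisio in facilitating implantation (Protocol 2.1, SAP 1.2). Protocol 2.1.3 says that its delivery cable is the part that releases the occluder, and enrolment is tied to an attempt with Trevisio. On that reading, success means success of that attempt. This stands as evidence of intent. It does not make release with Trevisio a condition of the endpoint, and SAP 1.4.1 offers its wording as the definition.

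A reader might go further and infer that the plan counts conversions as Trevisio successes. The documents do not support that. They are silent on conversions, and the places where a rule would naturally sit are redacted: the analysis populations (Protocol 8.1; SAP 2.1.1 and 2.1.2), text around the hypotheses, and the success criteria (Protocol 8.8). The case report forms are under separate cover (Protocol Appendix V).

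A reader might also infer that Trevisio failures would leave no record. That too goes beyond the text. Protocol 7.3.2 requires delivery system deficiencies to be reported on a dedicated form within 3 calendar days, and 6.2.1 collects ancillary product use and implant success or failure. What remains is that no visible text links these records to technical success, and the list in 6.2.1 does not name the system that achieved release.

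Finally, the size is open. Because Protocol 1.1 says that everything except the cable is identical to TorqVue, a failure caused by a shared component, by anatomy or by occluder sizing would not obviously be rescued by changing system. Low conversion fractions must therefore be considered, and at 10% the inflation is modest.

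**Conclusion.** The point holds as a gap in the visible definition: literal scoring would accept an occluder released by any delivery system after a Trevisio attempt, in both cohorts. It is not established that the sponsor intends to score conversions that way, or that conversions will be frequent.

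The firmest statement of size is that the pass mark allows only 4 failures per cohort at the minimum enrolments, so the scoring of a single subject can decide the result. The pass probabilities rest on an assumed exact test, assumed conversion fractions and a Trevisio-only rate set at the goal. They show sensitivity and are not forecasts. A larger enrolment would move the cut-offs.

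This should be fixed. Confidence is medium, because redacted text or the case report forms may already contain a rule.

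**What to change.** In Protocol 4.1, 8.2.1 and Appendix IX and in SAP 1.4.1 and 2.3.1, define technical success as deployment and release of at least one Amplatzer occluder by means of the Trevisio system, and state that completion with any other delivery system is a technical failure. If such a rule already exists in redacted text, carry it into the definition.

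State in advance how exchange for another Trevisio unit is scored, whether of the same or a different size, and tabulate these exchanges separately. That scoring is a separate choice, since the first unit may itself have failed.

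Confirm that the procedure case report form records the delivery system used at release, and add the field if it does not.

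The cost is a wording change in both documents and at most one data field. The observed success rate may be slightly lower.

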5.2 Subject Screening and Informed Consent

5.2.1 Subject Screening

Potential subjects and/or legal guardians of potential pediatric (minor) subjects presenting at the clinical sites will be fully informed about the clinical study, following the established Informed Consent process (described in Section 5.2.2). Once a duly dated and signed Information and Consent Form is obtained, the clinical study-specific screening procedures may begin. For potential subjects who are considered minors, an informed assent or consent process will be followed in accordance with EC requirements (described in Section 5.2.2.1) prior to commencement of study-specific screening procedures.

Subjects must be screened for clinical study eligibility by a member of the site's clinical study team previously trained to the CIP.

Patients being considered for PFO, ASD, or VSD closure with an Amplatzer occluder will be asked to sign an Informed Consent form if they wish to participate in the clinical study. Subject data will be collected following written, informed consent to participate in the clinical study. However, subjects will not be considered enrolled until they have met enrollment criteria as defined in Section 5.3.

In case the subject does not meet all study eligibility criteria after provision of Informed Consent, the subject will not be included in the study. The Principal Investigator or the delegated clinical study personnel will record the screening failure in the hospital records and on a screening log as required.

5.2.2 Informed Consent

The Principal Investigator or his/her authorized designee (only if the patient is considered a minor) will conduct the informed consent process, as required by applicable regulations and the center's EC. *Adults above the legal age of consent who choose to participate in the study must be able to provide their own written, informed consent (i.e., no authorized designee may sign on their behalf).* This process will include a verbal discussion with the patient or legally authorized representative (if the patient is a minor) on all aspects of the clinical study that are relevant to the patient's decision to participate, such as details of clinical study procedures, anticipated benefits, and potential risks of clinical study participation. The patient and the legally authorized representative must be informed about their right to withdraw from the clinical study at any time and for any reason without sanction, penalty or loss of benefits to which the subject is otherwise entitled. Withdrawal from the clinical study will not jeopardize their future medical care or relationship with the Investigator.

During the discussion, the Principal Investigator or his/her authorized designee will avoid any improper influence on the patient and will respect the patient's legal rights. Financial incentives will not be given to the patient. The patient or patient's legally authorized representative shall be provided with the Informed Consent form written in a language that is understandable to the patient and has been approved by the center's EC. The patient or legally authorized representative shall have adequate time to review, ask questions, and consider participation. The Principal Investigator or his/her authorized designee will make efforts to ensure that the patient and/or subject's legal guardian understands the information provided. If the patient and/or legally authorized representative agree(s) to participate, the Informed Consent form and appropriate assent form must be signed and dated by the patient and legally authorized representative and thereafter by the person obtaining the consent prior to any clinical study-specific procedures. The signed originals will be filed in the subject's hospital or research charts, and a copy will be provided to the subject and his/her legally authorized representative. Failure to obtain informed consent from a subject prior to clinical study enrollment should be reported to Sponsor within 5 working days and to the reviewing center's EC according to the EC's reporting requirements.

[REDACTED]

[REDACTED]

Clinical Investigation Plan

If, during the clinical study, new information becomes available that can significantly affect a subject's future health and medical care, the Principal Investigator or his/her authorized designee (if applicable) will provide this information to the subject and/or legally authorized representative. If relevant, the subject and/or subject's legally authorized representative will be asked to confirm their continuing informed consent in writing.

